This is a randomized, multicenter, double-blind, placebo-controlled phase III study (Clinicaltrials.gov identifier NCT 03158532) with an all-comers design, comparing the use of nitroglycerin to decrease the rate of radial artery occlusion after transradial catheterization. Using a 2-by-2 factorial design, we will randomly assign 2128 patients with a clinical indication for coronary angiography (ad hoc angioplasty allowed) or percutaneous coronary intervention (PCI) to receive either 500 micrograms of nitroglycerin or placebo (0,9% sodium chloride), administered intra-arterially through the sheath, in two different moments during transradial catheterization: shortly after the arterial sheath insertion and at the end of the radial procedure, before sheath removal. Written, informed consent will be obtained from each subject. The study protocol has been presented to the institutional medical ethical committee of all participating hospitals to comply with local standards.

Randomization and final acceptance into the study will take place after successful radial artery cannulation and guide wire advanced into the radial arterial lumen through the needle to allow exclusion of failed radial puncture.

Patient population

All eligible patients are aged 18 years or over with a clinical indication for coronary angiography (ad hoc angioplasty was allowed) or percutaneous coronary intervention (PCI) if the following pre-requisites are met: (i) choice of the operator to use the transradial access route and (ii) use of sheath size 5 or 6 French. Allen test was not obligatory performed. The exclusion criteria were: (I) primary angioplasty due to acute myocardial infarction; (ii) intubated patients; (iii) complications during procedure (cardiac arrest, pulmonary oedema, cardiogenic shock, and stroke); (iv) prior inclusion in this trial; (v) known allergy or intolerance to nitrates; (vi) patients medicated with continuous intravenous nitrates or whom received any nitrates on the last hour and (vii) use within 24 hours prior to randomization of phosphodiesterase inhibitors.

Outcomes

Primary outcome

RAO: incidence of radial artery occlusion as confirmed by the absence of antegrade flow in vascular high resolution duplex ultrasound, up to 24 hours after catheterization.

Secondary outcomes

Late RAO: incidence of radial artery occlusion as confirmed by the absence of antegrade flow in vascular high resolution duplex ultrasound, 30 days after catheterization.

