Comfort assessment: pain felt by the patient in the forearm, assessed using numeric pain rating scale. The 11-point numeric scale ranges from '0' representing one pain extreme (e.g. "no pain") to

'10' representing the other pain extreme (e.g. "worst pain imaginable"). Only the numbers themselves are valuable answers, meaning that there are only 11 possible answers in the 0–10 interval.

Spasm (operator evaluation): catheter friction, as experienced by the operator (subjective measure), on a predetermined score: 0. No resistance during catheter manipulation or pain reported by the patient; 1. No resistance during catheter manipulation, but with pain reported; 2. Light resistance during catheter manipulation; 3. Moderate to strong resistance during catheter manipulation; 4. Catheter trapping.

Procedure duration: total duration of the procedure, from sheath insertion to last catheter removal.

Radiation exposure: total radiation used in the procedure (mGy).

Study definitions

RAO: the absence of an antegrade flow in radial artery was recorded by doppler ultrasound study.

RAS: will be defined as spasm when: operator evaluation of spasm bigger than 2 by predefined scale; need of spasmolytic medication; access site conversion due to confirmed angiographic evidence of spasm.

Access site conversion: impossibility of complete procedure without another arterial site access. It may be due to spasm or anatomical reason, and should be confirmed with angiography.

Radial puncture attempt: defined as any skin puncture with positive blood draw through the needle.

Local hematoma: will be classified according to the EASY scale: I, ≤ 5 cm diameter; II, ≤ 10 cm diameter; III, > 10 cm but not above the elbow; IV, extending above the elbow; and V, anywhere with ischemic threat of the hand.

Major bleeding: will be graded according to the Bleeding Academic Research Consortium definition: Type 3 ((3a) bleeding with hemoglobin drop ≥ 3 and < 5 g/dL, or packed red cells transfusion; (3b)

bleeding with hemoglobin drop ≥ 5 g/dL, heart tamponade, bleeding requiring surgical intervention or bleeding requiring intravenous inotropic drugs; (3c) intracranial hemorrhage; subcategories confirmed by autopsy, imaging examinations or lumbar puncture; intraocular bleeding with vision impairment) or type 5 bleeding ((5a) possibly fatal bleeding, (5b) definitive fatal bleeding).

Transradial procedure

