study. Continuous variables will be described as means and standard deviation and compared using Student's t -test for normally distributed variables or assessed using Mann-Whitney test when not normally distributed. Categorical variables are expressed as frequencies and group percentage and will be compared with the chi-square or Fisher's exact tests. To test the interaction between interventions, we used a multivariable logistic-regression model that included the two randomized treatments and their interaction as parameters. In the analysis of the primary and secondary end points, a two-tailed p value of less than 0.05 will be considered statistically significant. No prespecified interim analysis will be performed. All analyses will be performed using SPSS version 22 (SPSS Inc., Chicago, Illinois).

Discussion

Cardiac catheterization is a common procedure and is need in many clinical scenarios and many times repeated procedures are need. The use of TRA is increasing aiming to improve patient comfort, save costs and reduce rates complications. This implies that the occurrence of RAO should be considered because, once it's occurred, it is impossible to use radial access for future catheterization. In most cases RAO occurs promptly after the procedure and up to 50% of patients have spontaneous recanalization of the artery within 1 month. A palpable pulse does not exclude the diagnosis of RAO: collateral blood flow may supply the periphery of the radial artery distally to the occlusion, giving a false impression of radial artery patency. Therefore, RAO can often be undiagnosed. Radial artery patency is better evaluated with clinical testing as the reverse Barbeau's test and with Doppler ultrasonography. Many interventions are suggested to reduce the risk of RAO, mainly anticoagulation, patent hemostasis and a bigger sheath-to-radial-artery ratio. Although nitroglycerin promotes vasodilation and thus improves the sheath-to-radial-artery ratio, no recommendation is done to its routinely use. Handling confounding factors such as anticoagulation and hemostasis, this test has an ideal design to address the question of whether routine use of the

nitroglycerin approach is superior to not use with respect to the occlusion occurrence, including possible predictors.

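### Procedure duration and radiation are compared without adjusting for the planned procedure, which costs precision, and no effect estimate with an interval is planned when Mann-Whitney is used

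*Combined protocol and SAP*

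**What the plan says.** Under Secondary outcomes, procedure duration is the "total duration of the procedure, from sheath insertion to last catheter removal", and radiation exposure is the procedure total in mGy. Each has one definition for all procedures.

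The Methods and Patient population sections admit patients with an indication for coronary angiography, with ad hoc angioplasty permitted, or for PCI. On timing, Methods states: "Randomization and final acceptance into the study will take place after successful radial artery cannulation". The indication is thus known before randomization. Whether an angiography becomes an ad hoc PCI is not.

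The Statistical analysis section has one rule for all continuous variables. They are described by mean and standard deviation and compared by a t-test if normal, or "assessed using Mann-Whitney test when not normally distributed". It names no stratum, no covariate and no effect measure. The only model is a logistic regression for the interaction of the two randomized treatments.

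**The concern.** Total time and total radiation can be expected to depend on whether an intervention is done as well as on how easily the catheter moves in the radial artery. A pooled two-sample test counts the difference between angiography and PCI as noise, although part of it is predictable from an entry criterion. The test then has less power for a nitroglycerin effect than the same data could give.

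The second matter is reporting. If the data are judged not normal, the planned result is a Mann-Whitney p value beside means and standard deviations. That p value does not test the difference in means, and no matching estimate or interval is planned. A reader could then not tell a small effect from an imprecise one.

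This concerns two of the five secondary outcomes.

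**Working it through.** **Inputs.** The documents give 2128 patients in a 2-by-2 design, so 2128/2 = 1064 on each side of a comparison of one dose with placebo, and a two-sided 0.05 level. They state no power, standard deviation or expected effect for duration or radiation, so there is no planned figure to reproduce; the 1064 was set for RAO. PCI share, PCI-to-angiography ratio, spread and effect are all assumed below.

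**Step 1: formula.** Set the within-type SD to 1. Let π be the PCI share and g the gap between PCI and angiography means in within-type SDs. Then

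- pooled SD = √(1 + π(1−π)g²);
- share of variance due to procedure type = π(1−π)g² / (1 + π(1−π)g²).

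If procedure type were fully adjusted for, the difference detectable with 80% power would be (1.960 + 0.842) × √(2/1064) = 0.121 within-type SD. At that same difference, the pooled t-test has power Φ(2.802/pooled SD − 1.960). For π = 0.5 and g = 1: pooled SD = √1.25 = 1.118, and Φ(2.506 − 1.960) = 71%.

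| g | variance share, π 20% to 50% | pooled power (adjusted = 80%) |
|---|---|---|
| 0.5 | 4% to 6% | 78% |
| 1 | 14% to 20% | 71% to 74% |
| 2 | 39% to 50% | 51% to 59% |
| 3 | 59% to 69% | 34% to 43% |

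Procedure type makes up half of the variance only when g = 1/√(π(1−π)): 2.0 at a 50% PCI share, 2.5 at 20%, 3.3 at 10%.

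**Step 2: simulation with the factor that can actually be used.** Step 1 treats the procedure performed as known. Only the planned indication is known at randomization, so ad hoc PCI stays as noise in the angiography stratum. Model: log duration = log(PCI ratio) × PCI + log(0.93) × treatment + normal error with SD 0.5; 1064 per side, 1500 trials per setting. Power in %:

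| planned PCI | ad hoc among the rest | PCI ratio | raw t | Mann-Whitney | stratified rank test | adjusted log model | gain over Mann-Whitney |
|---|---|---|---|---|---|---|---|
| 30% | 10% | 2.5 | 60 | 67 | 86 | 86 | 19 |
| 50% | 10% | 2.5 | 65 | 65 | 86 | 87 | 21 to 22 |
| 30% | 25% | 2 | 71 | 77 | 86 | 86 | 9 |
| 10% | 25% | 2.5 | 62 | 70 | 76 | 77 | 6 to 7 |
| 30% | 10% | 1.5 | 83 | 86 | 90 | 91 | 4 to 5 |

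The simulation error of one power figure is about √(0.65 × 0.35/1500) = 1.2 points, so the gain is about 4 to 20 points. With no effect (30%, 10%, ratio 2.5) all four methods reject in 4% to 5% of trials. Planned indication explained about 10% to 44% of the log variance over the settings tried.

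**Step 3: which dose.** Duration stops at removal of the last catheter. The Transradial procedure section places the second injection at the end of the procedure, before sheath removal. Only the start dose can plausibly change duration or radiation.

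**The case against.** An unadjusted comparison of randomized groups is legitimate. Randomization balances the indication in expectation, and all methods keep their type I error. Adjustment here is a matter of efficiency. The primary outcome is unaffected, and spasm and forearm pain are secondary outcomes in their own right, so an effect on spasm can be seen without duration or radiation. The size of the loss rests on assumed shares and an assumed 7% effect. With a 10% shortening, pooled Mann-Whitney already had 90% to 98% power in all six settings tried. All of this stands, and it limits the point to an inexpensive gain.

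Three stronger readings are tempting and are not supported:

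- **Procedure type dominates the spread.** The documents give no times or shares. Even in settings chosen with PCI 2 to 3 times as long and 30% to 50% planned, planned indication explained 15% to 44% of the log variance, less than half.
- **A real shortening would probably be reported as no difference.** In those same settings pooled Mann-Whitney had 56% to 76% power, so the assumed effect is found more often than missed. A stratified analysis can show an effect only if one exists.
- **An effect of radial access is being hidden.** Access is radial in every patient. The randomized contrast is nitroglycerin against placebo at two moments.

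It can also be said that a single ratio is hard to read if nitroglycerin affects only catheter handling, so that the proportional effect differs between indications. This is a fair limit on interpretation. Adjustment still gains power in that case.

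**Conclusion.** The point holds as a loss of precision and a gap in reporting. The plan pools angiography and PCI patients in an unadjusted test for two secondary outcomes, although the indication is available before randomization, and it plans no estimate with an interval when the rank test is used. The direction of the loss follows from the design: adjustment gained power in every non-null setting tried.

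Its size is conditional. The figure of about 4 to 20 points over pooled Mann-Whitney assumes a 7% shorter duration, within-type log SD 0.5, log-normal times and PCI lasting 1.5 to 2.5 times as long. It shrinks with few planned PCIs or a larger true effect. Radiation was not simulated; the same reasoning applies to it, but no figure is offered. The plan has no validity problem on this point, and no conclusion on RAO depends on it.

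**What to change.** For duration and radiation, replace the t-test or Mann-Whitney rule by one prespecified analysis:

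- a linear model on the log scale with start dose, end dose and the indication known at randomization (angiography or PCI), not whether ad hoc PCI was done, because that is decided afterwards;
- the start-dose contrast named as the comparison of interest;
- the result given as a ratio of geometric means with 95% CI;
- a rank test stratified by planned indication as sensitivity analysis;
- both variables described by median and quartiles within planned indication.

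The cost is SAP wording. The indication is already established for eligibility, and the model runs in SPSS, the package the plan names. There are two small downsides: a ratio replaces a mean difference, and one ratio averages over the indications if the effect differs between them.

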The use of the transradial approach (TRA) for coronary catheterization has increased over the years, worldwide. Radial artery is nowadays utilized by default for percutaneous coronary procedures in many centers, thanks to the reduced rates of vascular and bleeding complications and easier post-procedural management. The use of TRA also improves patient comfort, saves costs and it has an equivalent procedural success when compared to the femoral approach.

Although it is widely accepted by cardiologists and patients, some problems still exist. One of the major limitations is the development of radial artery spasm (RAS), which can reduce success rates, leading to femoral conversion, and cause significant pain to patients. The incidence of RAS varies between 2% and 34%. Aiming prevent RAS, the use of prophylactic intraarterial vasodilators is

routinely recommended by experts, mainly verapamil or nitroglycerin. Most catheterization laboratories habitually use some medication to prevent RAS, however, it is not a consensus.

Another important complication, often underestimated, is the post-procedural radial occlusion (RAO). Incidence of radial pulse loss has been reported to range from 1% to 12%. The benign nature of such an event has been constantly emphasized due to the dual blood supply to hand from the palmar arch. Mostly, the occurrence of radial occlusion is asymptomatic, symptomatic radial occlusion requiring medical attention occurred in only 0.2% of patients, but hand ischemia caused by RAO has been described. The most important aspect is that once artery is occluded, it can not be used neither as access site for future catheterization, nor be used as a conduit for bypass surgery nor fistula formation in hemodialysis patients. The use of small caliber catheters, adequate dose of heparin administration, immediate sheath removal after procedure, patent hemostasis technique and short time of compressive bandage are the key elements to reduce the risk of artery occlusion. Notably the presence of radial pulse does not exclude radial occlusion due to presence of collateral circulation; it can be more accurately evaluated by absence of antegrade flow in vascular doppler ultrasound. In fact, many operators do not assess radial artery patency before discharge.

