completion, the sheath is initially pulled by approximately 2 to 3 cm. The device is applied to the patient with the green marker (located in the center of the larger balloon) positioned exactly at the puncture hole to aid in the location, visualization and control of possible bleeding. The balloon is inflated with an adequate syringe injecting 15 ml of air with simultaneous and total sheath removal, resulting in the absence of active bleeding. If bleeding occurs, additional 3 ml of air is injected to obtain complete hemostasis. The device is then slowly deflated to the lowest allowable volume (minimum 7 ml) while maintaining hemostasis. If bleeding occurred, 1 ml of air was reintroduced from the bleeding point. Radial artery patency was evaluated utilizing plethysmographic and pulse oximetry evaluation, with sensor placed over the thumb or index finger, and occlusion (manual pressure) of the ulnar artery. Absence of plethysmographic waveform is indicative of interruption of radial artery flow. After 1 hour post diagnostic procedure or 2 hours post intervention, 3 ml of air is removed every 15 minutes. If bleeding occurs during any stage of device removal, the volume of air needed for hemostasis is again injected, restarting the deflation process 60 minutes later. When all the air is removed, and there is no bleeding, the device is removed and the access site is covered with a simple dressing. Dressing should not encircle the entire wrist.

Statistical analysis

The primary analysis of the study is a superiority comparison between the use of nitroglycerin to decrease RAO, in all randomized patients, based on the intention-to-treat principle.

Using our primary end point to estimate the sample size, we suppose to have a 30% reduction in RAO for each trial intervention, considering potential interaction between them. Estimating RAO prespecified in the primary outcome of approximately 11.7% without use of nitroglycerin, with an alpha level of 0.05 and a beta level of 0.20, the minimum estimated sample size per group was established as 1064 individuals. As we do not expect any subsequent loss of follow-up due to the short primary evaluation, the enrollment of 2128 patients would provide sufficient power to the

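### The only test on offer for the primary RAO comparison is unadjusted; prespecified adjustment for centre and sheath size is a cheap but small improvement, worth about 0 to 2 power points

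*Combined protocol and SAP*

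**What the plan says.** All references are to the Combined protocol and SAP.

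- **Endpoint (Primary outcome).** The endpoint is binary: "RAO: incidence of radial artery occlusion as confirmed by the absence of antegrade flow in vascular high resolution duplex ultrasound, up to 24 hours" after the procedure.
- **Test (Statistical analysis).** The primary analysis is a superiority comparison by intention to treat. No test is tied to RAO by name. The rule that covers a binary endpoint is "Categorical variables are expressed as frequencies and group percentage and will be compared with the chi-square"; the same sentence then offers Fisher's exact test. Both are unadjusted.
- **Model (Statistical analysis).** A logistic regression is specified that "included the two randomized treatments and their interaction as parameters". Its stated purpose is the interaction test. Centre and sheath size enter no model.
- **Determinants of RAO (Background).** The key elements in reducing risk begin with "The use of small caliber catheters, adequate dose of heparin administration", and the list also includes short compression.
- **What varies between patients.** Patient population requires "use of sheath size 5 or 6 French". Methods describes a multicentre trial, and no stratification factors are given.
- **Sequence.** Under Methods, randomisation follows passage of the guide wire into the artery. Under Transradial procedure, the sheath is then inserted and the first study dose is given through it.

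**The concern.** In a multicentre trial with a known prognostic variable on record, an unadjusted comparison gives up some precision. Without described stratification, centre and sheath size can also be unbalanced by chance. If imbalance is noticed after unblinding and only then adjusted for, the choice of model is open to challenge; a prespecified model avoids that.

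The plan also leaves open whether the chi-square compares the factorial margins or the four cells, and it names no effect measure or confidence interval. A stated primary model would settle these too.

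What is at stake is a little power and a clearer specification. Bias and type I error are not at issue.

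**Working it through.** **Inputs from the documents.** Control rate "approximately 11.7% without use of nitroglycerin"; effect: "we suppose to have a 30% reduction in RAO for each trial intervention, considering potential interaction between them"; two-sided alpha 0.05; power 0.80; 1064 per group; total 2128.

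**1. The plan's own figure.** With p1 = 0.117, p2 = 0.7 × 0.117 = 0.0819 and mean 0.09945:

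n = [1.96·√(2 × 0.09945 × 0.90055) + 0.8416·√(0.117 × 0.883 + 0.0819 × 0.9181)]² / 0.0351² = (0.8295 + 0.3556)² / 0.001232 ≈ 1140 per group, not 1064.

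Power at 1064: z = (0.0351 − 1.96 × 0.012975) / 0.012952 ≈ 0.747, giving 77.2%.

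If both interventions work multiplicatively, the factorial margins are 11.7% × (1 + 0.7)/2 = 9.945% and 0.7 × 9.945% = 6.96%. Then z = (0.029835 − 1.96 × 0.012061) / 0.012044 ≈ 0.514, giving 69.7%. These are the baselines. The shortfall from 80% is a separate sample-size matter.

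**2. The other randomised factor.** Its share of outcome variance is R² = [(0.09945 − 0.069615)/2]² / (0.08453 × 0.91547) = 0.0002225 / 0.07739 = 0.29%. Effective total: 2128 / (1 − 0.0029) ≈ 2134, or about 6 patients and 0.1 power point. The factors are orthogonal in a balanced factorial, so leaving one out causes no confounding.

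**3. Centre and sheath size, by variance explained.** The documents give no strengths, so R² is an assumption. With effective n = 1064 / (1 − R²) per group:

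| R² | Power, 11.7% vs 8.19% | Power, margins 9.95% vs 6.96% |
|---|---|---|
| 0 | 77.2% | 69.7% |
| 1% | 77.6% | 70.1% |
| 2% | 78.1% | 70.5% |
| 3% | 78.5% | 71.0% |
| 5% | 79.3% | 71.9% |

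For scale, at 10% overall RAO with half the patients on each size, a sheath-size relative risk of 2 means 6.67% vs 13.33%, so R² = 0.0333² / 0.09 = 1.2%. A between-centre SD of 3 percentage points gives 0.03² / 0.0774 = 1.2%. Reaching 80% at the planned rates would need R² ≈ 1 − 1064/1140 = 6.7%.

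**4. Simulation.** 2128 patients, 11.7% RAO on double placebo, relative risk 0.7 per factor, 10,000 runs per row. Assumed: four equal centres and a 50/50 sheath split. Entries are power (%) for one factor; both logistic models use Wald tests.

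| Centre SD (logit), sheath OR | Chi-square | Logistic, both factors | Logistic, plus centre and sheath | Full model minus chi-square | Full model minus two-factor model |
|---|---|---|---|---|---|
| 0, 1 | 70.50 | 70.38 | 70.20 | −0.30 | −0.18 |
| 0.3, 1.5 | 69.90 | 69.65 | 70.01 | +0.11 | +0.36 |
| 0.5, 2 | 69.39 | 68.83 | 69.74 | +0.35 | +0.91 |
| 0.8, 3 | 68.89 | 68.71 | 71.24 | +2.35 | +2.53 |

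The Monte Carlo SE of each power is √(0.7 × 0.3 / 10,000) ≈ 0.46 points. The comparisons are paired and so less noisy, but tenths of a point should not be read closely: 4,000 runs of the same four scenarios gave −0.4, +0.8, +1.2 and +2.4 against chi-square.

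A further like-for-like Wald simulation gave about −0.2 to +2 points, with a squared ratio of test statistics of 0.99 to 1.04. That equals about −21 to +85 patients (−0.01 × 2128 to 0.04 × 2128).

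**The case against.** The strongest reply is that the planned test is valid, the gain is marginal, and its size rests wholly on assumption. The documents give no number of centres, between-centre spread, sheath split or odds ratio. Heparin and haemostasis are set by protocol, which may narrow centre differences. If the covariates are not prognostic, adjustment loses a trace of precision. All of this stands, and it limits the point to a minor one.

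A reader might infer more than the documents support:

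- **That the plan fixes chi-square as the RAO test.** The rule is generic and includes Fisher's exact test. The unadjusted primary test is inferred from the absence of any other.
- **That ignoring the other factor is a serious fault.** A model containing both treatments is specified, though for the interaction only, and step 2 puts the cost at about 0.1 point.
- **That adjustment saves 40 to 115 patients.** Such a figure comes from setting a Pearson chi-square against a likelihood-ratio test. With every covariate effect at zero, that comparison still shows a squared ratio of 1.011, or about 0.011 × 2128 ≈ 23 patients that adjustment did not earn.
- **That planned procedure determines heparin and compression.** Transradial procedure ties the extra heparin to PCI being done, and Arterial hemostasis says "After 1 hour post diagnostic procedure or 2 hours post intervention, 3 ml of air is removed every 15 minutes". Both follow the procedure performed, and ad hoc angioplasty is allowed. Planned procedure is only a proxy, and nothing shows that it is recorded before randomisation.
- **That sheath size is a baseline value without qualification.** The sheath goes in after randomisation. Only the intended size, or the first sheath placed before study drug, is safe from influence by treatment.

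**Conclusion.** The point holds as a small matter of efficiency and specification. The only test offered for the primary endpoint is unadjusted, and centre and sheath size are left unused. Adjusting for them is worth about 0 to 2 power points over most of the assumed range. It gains about 2.5 only at a centre SD of 0.8 on the logit scale with a sheath odds ratio of 3, and nothing if neither variable is prognostic. These sizes depend on assumed covariate strengths, equal centres and an even sheath split, none of which is in the documents.

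It would be tempting to present adjustment as the answer to the trial's power of 77.2%, or 69.7% on the margins. The figures do not support that: the assumed settings leave power below 80% on either basis.

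**What to change.** Before unblinding, add a paragraph to Statistical analysis stating that:

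1. The primary test of each factor comes from a main-effects logistic regression, without the interaction term, containing both randomised factors, centre and sheath size (5 or 6 Fr).
2. Sheath size means the size intended at randomisation or the first sheath inserted before study drug, never a later exchange.
3. Small centres are pooled by a stated rule.
4. Planned procedure may be added only if recorded before randomisation. Ad hoc PCI is not adjusted for, because it is decided after the first dose.
5. The effect is reported as a standardised (marginal) risk difference and relative risk with 95% CI, so that the target is not a conditional odds ratio.
6. The unadjusted chi-square or Fisher's exact test on the factorial margins is a sensitivity analysis, and the interaction model serves the interaction test only.

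The costs are the paragraph, the pooling rule, a short standardisation step beyond the SPSS model fit, and a possible trivial loss of precision if the covariates prove non-prognostic. The documents do not say whether the data have been unblinded. The cover date (December 2024) is later than the expected end of inclusion (second half of 2019). If unblinding has occurred, the adjusted analysis should be labelled supportive.
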